2.3 Exploratory Objectives

Document categorical reasons stated by patient for discontinuation of apixaban, alternative anticoagulation measures used, and rate of discontinuation of the alternative anticoagulant. [Categorical reasons for discontinuation will include: Physician discretion, subject preference without physician oversight, bleeding complication, other suspected medication side effect, financial difficulties with obtaining drug, VTE recurrence on therapy, other reason.]

3 STUDY DESIGN

3.1 Overview of Study Design

Prospective, multicenter observational study, of the effectiveness of a standard of care protocol implemented to enhance home treatment of VTE. Study population will be selected as part of usual care as eligible for home treatment. Study personnel will travel to participating institutions to qualify the sites, deliver a Powerpoint® lecture to introduce the protocol, meet and train site principal investigators, emergency physicians and research personnel on the implementation of the protocol as part of usual clinical care, and data collection methods for a quality assurance registry with plans to use the data collected in this registry in future publications. Follow-up will be 30 days using medical records and/or telephone interview to assess for primary outcomes of bleeding or VTE recurrence.

3.2 Study Population

Emergency department patients with new or recurrent VTE deemed low-risk by modified Hestia or clinician discretion and sPESI (-).

3.2.1 Inclusion Criteria

Criteria for initial VTE diagnosis require a filling defect interpreted as positive on computerized tomographic pulmonary angiography, a ventilation-perfusion lung scan interpreted as high probability, or an incompressible vein observed on venous ultrasound of an extremity or jugular vein. Screening includes electronic surveillance of the “VTE home treatment order set” which ensures low risk criteria and then provides appropriate medication, including apixaban as an option, and discharge instructions. Enrollment occurs at the time of written informed consent.

1. Patients must be **low risk**, as defined by either A or B below:

A. The modified Hestia criteria:

- Systolic blood pressure > 100 mm Hg
- No thrombolysis needed
- No active bleeding
- SaO₂ >94% while breathing room air
- Not already anticoagulated
- No more than two doses of IV narcotics in the emergency department
- Other medical or social reasons to admit
- Creatinine clearance >30mL/min
- Not pregnant, severe liver disease or heparin induced thrombocytopenia

OR

B. The physician opinion that a patients' overall social and medical situation is favorable for home treatment and the patient has a zero score on the simplified pulmonary embolism severity index (sPESI).

All of the following must true:

- Age < 81 years
- No history of cancer
- No history of heart failure or chronic lung disease
- Pulse < 110 beats/min
- SBP > 99 mm Hg
- O₂ sat >89%

We have chosen either criteria because both have been found equal in terms of safety for outpatient treatment of PE.^{6,22} Hestia includes implicit questions that most emergency physicians would use as criteria for discharge (e.g., overall medical status and social situation), whereas sPESI does not. For that reason, we have added the additional gestalt assessment question about physician discretion.

[figure not shown]
2. Patients must be discharged in <24 hours after triage in an ED visit with diagnosis of VTE using objective criteria in the emergency department.

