1 INTRODUCTION

1.1 Study Rationale

This work seeks to generalize a protocol to improve the transition of care of patients with venous thromboembolism (VTE, including both deep vein thrombosis, DVT, and pulmonary embolism, PE) from the emergency department (ED) to home treatment. We hypothesize a <2% rate of 30 day re-hospitalization for recurrent VTE or bleeding in patients selected as low risk by the modified Hestia criteria or physician discretion and sPESI negative. The 2% upper limit of the 95% CI threshold is justified based upon data from AMPLIFY and pooled data from EINSTEIN DVT and PE which show a point estimate 30 day VTE recurrence rate of 1-1.2%.^{1,2} For patients deemed low risk in the present study, it can reasonably be predicted this rate will be considerably lower. The 30 day incidence of major bleeding were <1.0% in both AMPLIFY and EINSTEIN, and for patients with low risk of bleeding, the rate can be expected to be about 0.5% with upper limit 95% CI <1.0%.³ Additionally, the 90 day incidence of the composite rate for VTE recurrence and major bleeding reported in systematic reviews and meta analyses of outcomes of low risk VTE patients diagnosed in the ED and treated at home with vitamin K antagonists (VKAs) was 18/785 (2.2%, 95% CI 1.4-3.6%).^{4,5} Den exer et al randomized 275 Hestia negative patients to be treated with VKAs at home; 90 day follow up found 3 with recurrent VTE and 3 with major bleeding (6/275, 2.2%).⁶ Taken together, we submit these data which support the assertion of the upper limit 30 day failure rate (composite of VTE recurrence and bleeding) <2.0% to constitute a reasonable and prudent expectation of standard care. Recent evidence indicates the safety and acceptance of home treatment of both DVT and PE.^{7,8} Patient interviews indicate a strong patient preference to this approach over use of injectable low molecular weight heparin and vitamin K antagonists (e.g., <https://iu.box.com/riva-patient-interviews>). However, clinicians remain reluctant to discharge DVT and PE patients because lack of a “hard wired” system to guarantee patient follow-up⁹. **To help facilitate this transition in care**, in 2013 in Indianapolis, the project leader/principal investigator, implemented an outpatient treatment protocol using target specific anticoagulants (TSA) for patients with VTE in two hospitals with a low risk of treatment failure and drug related side effects. Most importantly, this included two dedicated clinics (known locally as the KLOT clinics) for these patients to follow-up. Two manuscripts describing the outcomes of the first 106 subjects, as well as a case-control cost effectiveness study have been published.^{10,11} A third paper documented good patient outcomes and quality of life equal to patients treated with usual care.⁹ With more experience, we have found the transition of care can occur from the ED to primary care physicians and even to existing anticoagulation clinics.

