2 OBJECTIVES

2.1 Primary Objectives

Evaluate the primary effectiveness of an implementation protocol to identify and manage care of patients diagnosed with DVT and/or PE who are discharged from the ED and treated with apixaban. Treatment failure rate, defined as the numerator, comprising the sum of subjects treated in this protocol who are re-hospitalized for >24 hours within 30 days of enrollment for either objectively diagnosed VTE or for major or clinical relevant non-major bleeding related event, divided by the denominator of enrolled subjects. Protocol success will be defined by the upper limit 95% CI for this proportion < 2.0%.

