3.4 Definitions of Study Variables

Recurrent VTE

1. Pulmonary embolism
 - a (new) intraluminal filling defect in segmental or more proximal branches on CT,
 - a (new) intraluminal filling defect or an extension of an existing defect or a new sudden cutoff of vessels more than 2.5 mm in diameter on the pulmonary angiogram,
 - a (new) perfusion defect of at least 75% of a segment with a local normal ventilation result (high-probability) on ventilation/perfusion lung scintigraphy.

- inconclusive CT, Pulmonary Angiography, or lung ventilation/perfusion scintigraphy with demonstration of DVT in the lower extremities by compression ultrasound or venography (Recurrent PE is not diagnosed by CT or ventilation/perfusion scans showing unchanged filling defects compared with the study qualifying images):

OR

2. Suspected (recurrent) DVT with one of the following findings if there were no previous DVT investigations:
 - abnormal compression of a deep vein, including calf, gastrocnemius, saphenous vein, femoral, brachial, axillary or jugular veins on ultrasound
 - an intraluminal filling defect on venography:

OR

3. Suspected (recurrent) DVT with one of the following findings if there was a DVT investigation at screening:
 - abnormal compression ultrasound where compression had been normal or, if non-compressible during screening, a substantial increase (4 mm or more) in diameter of the thrombus during full compression,
 - proximal extension of an intraluminal filling defect, or a new intraluminal filling defect, or proximal extension of non-visualization of veins in the presence of a sudden cut-off on venography

(Recurrent DVT is not diagnosed with compression abnormalities in the same vein as was abnormal on the study qualifying ultrasound).

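### The ultrasound rule for the index event does not require a deep vein, and the recurrence definition lists the saphenous vein as deep, so neither matches the DVT and/or PE objective

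*Protocol*

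**What the plan says.** Protocol 1.1 defines the disease as "venous thromboembolism (VTE, including both deep vein thrombosis, DVT, and pulmonary embolism, PE". The research question in 1.2 is about acute PE and/or DVT. The primary objective in 2.1 concerns "patients diagnosed with DVT and/or PE who are discharged from the ED and treated with apixaban".

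The imaging rule that makes this operational is in 3.2.1. It begins "Criteria for initial VTE diagnosis require a filling defect interpreted as positive on computerized tomographic pulmonary angiography", adds a high-probability lung scan, and ends with "an incompressible vein observed on venous ultrasound of an extremity or jugular vein". The second numbered inclusion condition asks for "diagnosis of VTE using objective criteria in the emergency department". No exclusion in 3.2.2 mentions superficial thrombosis.

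For the outcome, 3.4 item 2 applies to suspected DVT when there was no previous DVT investigation. It accepts "abnormal compression of a deep vein, including calf, gastrocnemius, saphenous vein, femoral, brachial, axillary or jugular veins on ultrasound". Item 3 applies when there was a DVT investigation at screening and names no veins.

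Sections 2.1 and 4.1.1 set the denominator as enrolled subjects. Success is an upper 95% confidence limit below 2.0%.

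**The concern.** The objective is stated for deep vein thrombosis and PE, but the test that admits a subject on ultrasound does not separate deep from superficial veins. A site that applies the clause literally could enrol an isolated superficial limb thrombosis. The recurrence definition does say deep, so the boundary was in mind, but its list then includes a vein of the superficial system (general anatomy; the protocol does not say so). No clean line is drawn at entry or at outcome.

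The stake is what a passing result means. Section 1.1 justifies the 2.0% limit from DVT and PE populations. If the denominator holds subjects outside that population, or the numerator holds events outside it, the proportion no longer answers the question in 1.2. The two slips can act in opposite directions: superficial index cases may add subjects with few failures, while saphenous-only recurrences may add failures.

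**Working it through.** **Inputs from the protocol.** N = 850 and a planning scenario of 3 recurrences plus 3 major hemorrhages, so 6/850 = 0.71% (4.2). Exact binomial interval and success limit of 2.0% (4.1.1). I take the interval as two-sided, which the protocol does not state.

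**Inputs assumed.** The share f of isolated superficial index cases, and their failure rate as a multiple r of the DVT/PE rate. The protocol gives neither. I show f from 0 to 30%, with r = 0 and r = 0.5. The value 0.5 corresponds to the same bleeding but no recurrence, given the planned 3 + 3 split.

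**Step 1: reproduce the plan's figure.** The exact upper limit for x failures in n is the 97.5% quantile of Beta(x+1, n−x).

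- 6/850: 1.53% (4.2 prints 1.5; agrees)
- 7/850: 1.69%
- 8/850: 1.85% (4.2 prints 1.8)
- 9/850: 2.0004% (4.2 prints 1.9; does not reproduce, a separate matter)

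At most 8 failures pass.

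**Step 2: remove superficial cases from the denominator, assuming none of them failed.** The result reverses at the largest n for which the upper limit is no longer below 2.0%.

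| Failures | Reverses at n ≤ | Removed | Share of 850 |
|---|---|---|---|
| 8 | 784 | 66 | 7.8% |
| 7 | 717 | 133 | 15.6% |
| 6 | 649 | 201 | 23.6% |

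**Step 3: chance of success with superficial cases included.** The mixed rate is p × [(1 − f) + r × f], and the chance of success is P(X ≤ 8) for Binomial(850, mixed rate). At p = 0.71%:

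| f | r = 0 | r = 0.5 |
|---|---|---|
| 0% | 0.848 | 0.848 |
| 5% | 0.877 | 0.863 |
| 10% | 0.903 | 0.877 |
| 20% | 0.945 | 0.903 |
| 30% | 0.972 | 0.926 |

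At a DVT/PE rate of exactly 2.0%, the chance of declaring success is 1.2% with f = 0. It becomes 3.1% at f = 10% and 7.4% at f = 20% with r = 0, or 1.9% and 3.1% with r = 0.5.

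**Step 4: the opposite direction.** Suppose 3.4 item 2 added saphenous-only recurrences to the planned 6 failures. Three of them give 6 + 3 = 9 failures, upper limit 2.0004%, and the result fails. So the saphenous entry can turn a passing result into a failing one, just as superficial index cases can do the reverse.

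**The case against.** The strongest reply is that the clause must be read with its governing sentence. It lists criteria for a VTE diagnosis, 1.1 defines VTE as DVT and PE, 2.1 repeats that limit, and the second inclusion condition again requires VTE. On that reading a superficial case enters only if a clinician first labels it VTE. This has weight: the protocol does not instruct sites to enrol superficial thrombosis. It does not remove the point. The second condition relies on objective criteria, and for the index event the only ones given are those in 3.2.1. A multicenter study that finds patients through an order set needs the boundary in the imaging rule itself.

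A reader might also infer that the loose wording dilutes the failure rate toward success. The documents do not support that. They give no superficial share and no lower failure rate for such cases. A zero rate is hard to defend, because these subjects would be on apixaban and bleeding that leads to a stay over 24 hours is a failure (3.4.1); half of the planned failures are bleeds. It would also be wrong to start from the 1 to 1.2% in 1.1, which is a recurrence rate from cited trials that the protocol expects to be considerably lower in low-risk patients.

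The saphenous entry is narrower than it looks. It applies only without a previous DVT investigation, for example a PE found on CT with no limb ultrasound. A subject enrolled on a limb ultrasound would ordinarily fall under item 3. The event must also lead to a stay over 24 hours. Where it applies it adds failures, which works against dilution.

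**Conclusion.** The mismatch in wording is certain. The entry rule in 3.2.1 is wider than the DVT and/or PE objective, and 3.4 item 2 counts a superficial vein as deep. This follows from the text and needs no assumption about case mix.

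The effect on the primary result is conditional, and its net direction is not known. Under the assumption most favourable to dilution (superficial cases never fail), the planned 6-failure scenario reverses only if about 24% of the 850 are superficial. Near the limit, about 8% is enough with 8 failures. At the planned rate, a 10% share moves the chance of success by 3 to 6 percentage points. The point deserves correction because small shares matter when the result is close to the limit and because the repair is cheap. It does not show that the study is biased toward success.

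**What to change.** - In 3.2.1, require an incompressible deep vein of an extremity, or an incompressible jugular vein, and say that isolated superficial vein thrombosis does not qualify.
- In 3.4 item 2, reconcile the saphenous entry with that rule, so that one statement of which veins count serves both index event and recurrence.
- Record the qualifying vein on the case report form. For subjects already enrolled, classify it from the ultrasound report.
- Keep enrolled subjects as the primary denominator, as 2.1 and 4.1.1 state. Removing subjects afterwards would contradict that rule, and deleting an outcome category during the study could only remove failures.
- Report the primary proportion and its exact interval with and without isolated superficial index events, and with and without saphenous-only recurrences.

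The cost is short amendments in two sections, a small amount of chart review and one sensitivity analysis.

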3.2.2 Exclusion Criteria

- VTE diagnosis while taking anticoagulants with evidence of compliance (e.g., physician opinion that patient is taking a Eliquis®, Xarelto® or Pradaxa®, low molecular weight heparin injections or warfarin as prescribed for any condition)
- Sensitivity or contraindication to use of apixaban
- Physician judgment that bleeding risk is high OR Ruiz-Gimenez (RIETE) score >2.³
<https://www.mdcalc.com/riete-score-risk-hemorrhage-pulmonary-embolism-treatment> (Note that several criteria are already excluded by Hestia):
 - Recent major bleeding, 2 points
 - Creatinine levels >1.2 mg/dl, 1.5 points
 - Anemia, 1.5 points
 - Cancer, 1 point
 - Clinically overt PE, 1 point
 - Age >75 years, 1 point

3.3 Data Source/Data Collection Process

The figure below demonstrates the data flow process. Each site will complete an electronic case report form that will be linked by a study ID (e.g. CMC001) to the study site enrollment registry, maintained at the study site. The study deliverable is a PHI deidentified REDCap data set (appendix). Placards will be posted in the emergency department with a flow diagram similar to the one diagrammed above. Each site will create a specific “VTE home treatment” order set which prints prescriptions. Subjects will follow-up in designated anticoagulation centers or with a primary care physician. The duration of anticoagulation will usually be at least 3 months.(16) Patients will be identified by query of the electronic order set. Outcomes will be assessed by medical record review and/or a telephone call to each patient made after 30 days after discharge from the emergency department to document outcomes from the time of discharge to 30 days thereafter.

The primary efficacy and safety aims will be assessed by telephone survey and medical record review at or after 30 days, asking the subject explicitly about any change in health status, any unscheduled visit to an emergency department or other healthcare provider, re-hospitalizations, VTE diagnoses, or bleeding events. The script and procedures for the phone call, including handling disconnected numbers, and non-answers will be in the guidance document.

Definitions of recurrent VTE: Study personnel will perform a chart review to confirm suspected recurrent PE/DVT, which will require explicit radiographic or ultrasonic evidence of PE/DVT.

The definition of **re-hospitalization for bleeding** requires chart review demonstrating explicit written decision-making by the admitting emergency physician that a patient was admitted (requiring >24 hour stay) for medical or procedural care to manage objective or suspected bleeding. This would include charted evidence of initially suspected but later disproven bleeding such as gastrointestinal bleeding. Bleeding events will be further characterized as **major bleeding or clinically relevant non-major bleeding**, using published criteria, further defined in the guidance document and using previously established criteria.^{3,21}

Secondary objectives

Discontinuation of apixaban. During the follow-up telephone call, patients will be asked if they discontinued apixaban and if so, what anticoagulant they are currently taking.

Capture rate and change in percentage of VTE patients discharged home. The percentage of all VTE (DVT and PE) discharged and change in percentage from pre- to post-implementation will be determined by search of billing records for ICD-10 coding for the immediate 3 months prior to and then 3-6 months after protocol start date.

Exploratory aims

Reason for discontinuing apixaban. Patients will be asked if they are still taking apixaban, and if the answer is no, they will be asked why not and the answer will be documented verbatim. This will be cross-checked by the site PI with the medical record and categorized by the site PI as 1. Bleeding, 2. other side effect, 3. change in diagnosis, 4. new contraindication, 5. patient elected, 6. Physician decision, not otherwise explained, or 7. other

Adverse event investigation. Chart review to investigate possible adverse events will be triggered by subject response to the question about change in health status at the 30 day follow up.

Other publication data for the CRF will be obtained by electronic chart review as previously described.²⁴

A PHI stripped eCRF will be populated by study personnel and concatenated with other sites for analysis.

All sites will sign a **data use agreement** that specifies control of data and publication plan.

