3.4.1 Outcomes/Endpoint Variables

The primary outcome measures the frequency of one or more episodes of a subject returning for medical care resulting in hospital stay > 24 hours as a direct result of either recurrent VTE or major or clinical relevant non-major bleeding within 30 days of VTE diagnosis that initiated enrollment. For the purpose of this protocol, these events are synonymous with the term treatment failure endpoints. Each case requires medical documentation indicating the reason for hospitalization was for treatment, diagnosis or monitoring of the recurrent VTE or bleeding condition. For example, if a subject returns to an emergency department for chest pain, and reports a nosebleed on the same day, and is hospitalized for testing related to the chest pain, and is not found to have recurrent VTE, the subject does not meet a primary failure endpoint. However, if the subject were admitted for nose packing, or was discovered to have a new PE, then in either case, the subject would meet the primary failure endpoint.

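### Section 3.3 counts admissions for later-disproven bleeding and requires an emergency physician's written decision; sections 2.1, 3.4.1 and 4.1 do neither, and nothing says which rule sets the primary numerator

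*Protocol*

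**What the plan says.** Section 3.3 gives what it calls the definition of re-hospitalization for bleeding. Chart review must show "explicit written decision-making by the admitting emergency physician" that the patient was admitted for more than 24 hours "for medical or procedural care to manage objective or suspected bleeding". The next sentence extends this to bleeding that did not occur: "This would include charted evidence of initially suspected but later disproven bleeding such as gastrointestinal bleeding". Only then comes the severity step, which begins "Bleeding events will be further characterized as" and names the major and clinically relevant non-major classes, with criteria in a guidance document.

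Section 3.4.1 defines the primary outcome as a stay of more than 24 hours that results directly from "either recurrent VTE or major or clinical relevant non-major bleeding within 30 days". For evidence it asks only for medical documentation of the reason for the stay. Sections 2.1, 4.1 and the first sentence of 4.1.1 use the same two bleeding classes. The research question in 1.2 and the success sentence of 4.1.1 say bleeding with no severity qualifier.

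Success means an exact binomial 95% upper limit below 2.0% (2.1 and 4.1.1). Section 4.2 plans on N = 850 with 3 recurrences and 3 major hemorrhages.

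**The concern.** The two definitions differ in both directions. Section 3.3 is wider because it counts an admission for suspected bleeding that is later ruled out; bleeding that did not occur cannot be major or clinically relevant non-major. Section 3.3 is also narrower because it needs the admitting emergency physician's written reasoning. Neither definition is a subset of the other, so following the stricter one does not resolve the difference.

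The numerator feeds the protocol's only pass/fail criterion, and few events are expected. If the rule is not fixed in advance, sites may code the same kind of admission differently, or the rule may have to be settled once the events are known.

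**Working it through.** **1. The definitions side by side**

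| | Section 3.3 | Sections 2.1, 3.4.1, 4.1 |
|---|---|---|
| Length of stay | >24 h | >24 h in 2.1 and 3.4.1; 4.1 says hospitalization |
| Bleeding that counts | Objective or suspected | Major or clinically relevant non-major |
| Bleeding later disproven | Counted expressly | Fits neither class |
| Evidence | Admitting emergency physician's written decision | Medical documentation of the reason (3.4.1) |

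Two cases show the effect:
- **Case A:** a stay of more than 24 h from the emergency department for suspected gastrointestinal bleeding that is then ruled out. It is a failure under 3.3 and not under 3.4.1.
- **Case B:** a direct admission of more than 24 h for a real major bleed, documented by a ward physician. It is a failure under 3.4.1 and not under 3.3.

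The worked example in 3.4.1 points towards confirmed events. A patient admitted for chest pain testing and not found to have recurrent VTE is not a failure. That example concerns suspected VTE, however, and does not address disproven bleeding.

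**2. How many failures the criterion allows**

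Inputs: N = 850 (4.2), exact binomial 95% interval (4.1.1), threshold 2.0% (2.1). The two-sided Clopper-Pearson upper limit is U(x) = Beta⁻¹(0.975; x + 1, 850 − x).

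The plan's own scenario is 3 + 3 = 6 failures. U(6) = 1.53%, which agrees with the 1.5 printed in 4.2.

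| Failures | Exact upper limit | Below 2.0%? |
|---|---|---|
| 6 | 1.53% | yes |
| 7 | 1.69% | yes |
| 8 | 1.85% | yes |
| 9 | 2.0004% | no, barely |
| 10 | 2.15% | no |

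At most 8 failures meet the criterion. The table in 4.2 prints 1.9 for 9 failures. That does not match the exact limit and is a separate error.

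**3. What disproven-bleeding admissions would do**

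The documents give no rate for them, so these counts are assumptions.
- From 6 failures: adding 1, 2, 3 or 4 gives 7, 8, 9 or 10 failures, with limits of 1.69%, 1.85%, 2.0004% and 2.15%.
- From 8 failures: adding 2 gives 10, and the limit moves from 1.85% to 2.15%.

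**4. Effect on the chance of success**

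P(success) = P(X ≤ 8), with X binomial(850, p). At p = 6/850 = 0.71% this is 0.85. If disproven-bleeding admissions add an assumed 0.1, 0.2 or 0.3 percentage points (850 × 0.001 = 0.85, 1.7 or 2.55 expected patients), it falls to 0.75, 0.63 or 0.52.

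**5. Secondary: recurrent DVT in 3.4**

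Item 3 accepts, "if non-compressible during screening, a substantial increase (4 mm or more) in diameter of the thrombus during full compression". The closing parenthesis says: "Recurrent DVT is not diagnosed with compression abnormalities in the same vein as was abnormal on the study qualifying ultrasound". A vein that could not be compressed at screening is a vein that was abnormal on the qualifying ultrasound, so read literally the parenthesis removes the 4 mm criterion. The corresponding PE parenthesis is limited to unchanged defects; the DVT one is not.

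**The case against.** The strongest reply is that 3.3 describes two steps: first capture every admission for possible bleeding, then classify it by severity, with 3.4.1 alone setting the endpoint. The endpoint text is also somewhat broad. Section 2.1 speaks of events related to bleeding, and 3.4.1 admits stays for diagnosis or monitoring. This softens the conflict without removing it. Section 3.3 calls its rule the definition, does not make the severity step a condition for counting, and gives disproven bleeding no class. It leaves the severity criteria to the guidance document (not shown), but settles the disproven case itself. Section 3.4.1 still requires the stay to result directly from bleeding of one of the two classes.

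Several limits on the point do stand:
- A reader might infer that one or two classifications decide the result. That needs 7 or 8 other failures first, against a planned 6. One added to 8, or two added to 7, stops at 9 failures, only 0.0004 percentage points over the line. With 851 subjects the limit for 9 would be 1.9981%, a success.
- A reader might infer that the wording favours the sponsor. Counting disproven bleeding adds failures and makes success harder, while the emergency-physician requirement can remove them. The net direction is unknown.
- The emergency-physician difference matters only for admissions that lack that physician's note, and the documents do not say how common these are.
- The DVT parenthesis can be read as excluding mere persistence, with the 4 mm rule still in force. It is a drafting conflict with no shown effect on the result.

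**Conclusion.** The contradiction is in the protocol's own text and affects the primary numerator. The same admission can be a failure under 3.3 and not under 2.1, 3.4.1 and 4.1, or the reverse, and no section ranks the two.

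The size is conditional. The criterion allows at most 8 failures in 850, which leaves 2 above the planned 6. Assuming the planned 6 occur, 3 disproven-bleeding admissions reach the threshold (2.0004%) and 4 clearly exceed it (2.15%). Assuming 8 other failures, 2 clearly exceed it. The documents do not show that such admissions will occur in these numbers, or that anyone intends to choose the rule after seeing the events. They show only that the rule is not fixed. The DVT wording is secondary.

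**What to change.** Before outcomes are reviewed, state one bleeding-failure rule and use it in 1.2, 2.1, 3.3, 3.4.1, 4.1 and 4.1.1, with the guidance document aligned.

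- One workable rule is to count a stay of more than 24 hours for bleeding confirmed as major or clinically relevant non-major, documented by any treating clinician and by any route of admission.
- Tabulate later-disproven bleeding admissions separately, and give a sensitivity analysis that adds them to the numerator.
- If the sponsor prefers the 3.3 rule, say that it governs and report the other as the sensitivity analysis. Either choice resolves the contradiction.
- In 3.4, reconcile the closing DVT parenthesis with item 3, for example by limiting it to unchanged abnormalities, as the PE parenthesis does.

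The cost is wording in those six sections and in 3.4, an aligned guidance document, one table row and one extra confidence interval. Sample size and patient care do not change.
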